# **FULL PROTOCOL TITLE: The Impact of Contact Lens Coefficient of Friction (CoF) on the Development of Lid Wiper Epitheliopathy (LWE)**

## **1.0 Objectives**

The primary study objectives are to determine the amount of Lid Wiper Epitheliopathy (LWE) induced in subjects after contact lens fitting that do not have LWE at study enrollment. Subjects in the trial will be fit in 2 contact lenses with different coefficients of friction (CoF). One eye will be fit in a contact lens with a low coefficient of friction (Acuvue Oasys®, Johnson & Johnson Vision, Jacksonville FL) while the contralateral eye will be fit in a contact lens with a high CoF (Air Optix® Night & Day® Aqua, Ft. Worth, TX), as reported in the scientific literature. The eye receiving each lens will be assigned randomly. The presence of LWE will be assessed at 2 different time points:

- Approximately 2 hours after contact lens fitting and
- After 7( $\pm 2$ ) days of contact lens wear

**Study Hypotheses:** Contact lenses with a greater coefficient of friction will induce a greater amount of LWE than contact lenses with a lower coefficient of friction. The presence of LWE will be assessed at 2 different study time points. As such, the following hypotheses will be tested:

After one week of contact lens wear

- $H_{01}$ : There is no statistically significant difference in the amount of LWE between contact lenses with different coefficients of friction
- $H_{a1}$ : There is a statistically significant difference in the amount of LWE between contact lenses with different coefficients of friction

After 2 hours of contact lens wear

- $H_{02}$ : There is no statistically significant difference in the amount of LWE between contact lenses with different coefficients of friction
- $H_{a2}$ : There is a statistically significant difference in the amount of LWE between contact lenses with different coefficients of friction

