## **FULL PROTOCOL TITLE: The Impact of Contact Lens Coefficient of Friction (CoF) on the Development of Lid Wiper Epitheliopathy (LWE)**

While CoF is a useful laboratory metric, it cannot be measured clinically. Therefore, a clinical corollary for CoF may be useful in determining which contact lens materials will minimize the potential for contact lens dropout. A possible clinical corollary for CoF is Lid Wiper Epitheliopathy (LWE), which has been reported to be related to contact lens discomfort. LWE leads to a loss of superficial epithelial cells in the lid wiper region of the eyelid. If CoF is indeed related to contact lens discomfort, subjects wearing a high CoF lens could potentially develop greater amounts of LWE compared to that observed with a low CoF lens.

While previous studies have determined the amount of LWE present in habitual contact lens wearers and non-contact lens patients, it is currently unknown how quickly LWE may develop in patients after contact lens fitting. Development of LWE in the post-contact lens fitting period may allow clinicians to predict the potential for contact lens discomfort and future dropout. This pilot study will collect data examining the development of LWE in the period immediately following contact lens fitting (2 hours post-fit) and after approximately 1 week of contact lens wear, corresponding to the time for a typical post-contact lens fitting assessment in clinical practice.

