### **3.0 Inclusion and Exclusion Criteria**

Potential study subjects must meet the following study inclusion criteria:

1. Must be able to read and understand the study informed consent
2. Must be a minimum of 18 years of age and less than 46 years of age at study enrollment
3. Must be healthy non-soft contact lens wearers (neophytes), or experienced contact lens wearers that have not worn their contact lenses for a minimum of 7 days
4. Have a spherical equivalent refractive error between -0.75 to -6.50DS at the spectacle plane
5. The subject must be able to attend study visits at the prescribed visit times and adhere to the study instructions

Potential study subjects cannot meet any of the following study exclusion criteria:

1. Pregnant and/or lactating females by self-report
2. Presence of current LWE on the upper eyelid (>0.5 in height or width)
3. Has greater than -1.00DC of refractive cylinder
4. Has greater than 1.00D of anisometropia
5. Is aphakic
6. Has clinically significant corneal or conjunctival staining that would prevent contact lens fitting, as assessed with sodium fluorescein dye

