### Sequence of Events

## FULL PROTOCOL TITLE: The Impact of Contact Lens Coefficient of Friction (CoF) on the Development of Lid Wiper Epitheliopathy (LWE)

Note: Contact Lens wearing subjects should report to Visit 1 after discontinuing SCL wear for at least 7 days. Subjects should report to the visit wearing their habitual vision correction.

Visit 1.1: Screening, Enrollment and Baseline		
Step	Item	Details
1.1.1	Informed Consent	Review and complete the informed consent form
1.1.2	Subject Demographics	Collect subject demographic data
1.1.3	History	Collect subject history
1.1.4	Concomitant Medications	Collect information on concomitant medications
1.1.5	Habitual Contact Lens Information	For CL subjects, review habitual lens information and verify that they have discontinued lens wear for at least 7 days
1.1.6	Preliminary Review of Inclusion/Exclusion Criteria	Review Inclusion/Exclusion Criteria for subject study eligibility
1.1.7	Distance Visual Acuity	Perform Distance, High Contrast Visual Acuity using Snellen optotype, OD/OS with the patient's habitual correction.
1.1.8	Questionnaires: Ocular Surface Disease Index (OSDI)	All Subjects: Administer the OSDI 
 
• If OSDI scores is <math>\geq 23</math>; skip to 2.9, Final Evaluation
 

1.1.9	Auto-refraction	Perform auto-refraction and record the refractive error and keratometry readings
1.1.10	Oculus Keratograph	Perform the following procedures using Oculus Keratograph, OD/OS 
 
• Non-invasive Tear Break Up Time (NITBUT)
 
• Tear Meniscus Height
 

1.1.11	Phenol Red Thread	Perform Phenol Red Thread test without anesthesia, OD/OS.
1.22	Ocular Surface Tear Collection	Collect 10 $\mu$ L surface tears using a microcapillary tube.
1.1.12	Slit Lamp Exam with vital dye staining/LWE evaluation	Instill 1 drop of NaFL + Lissamine Green Combination Drop, wait 5 minutes, instill an additional drop, wait 1 minute, then evaluate slit lamp findings using the CCLRU grading scale and evaluate LWE

**FULL PROTOCOL TITLE: The Impact of Contact Lens Coefficient of Friction (CoF) on the Development of Lid Wiper Epitheliopathy (LWE)**

		
 
• If no LWE is observed in both eyes, skip to Step 2.9: Final Evaluation and discontinue the subject from the trial
 
• If LWE is observed in either eye, continue to Step 1.1.13: Digital Photography
 

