1.1.13	Digital Photography	Perform Digital Photography of the Lid Wiper region OD/OS
1.1.14	Subjective Refraction	
Perform Manifest Refraction using maximum plus to best visual acuity.
 
 
• If the subject has <math>> 1.00\text{D}</math> refractive cylinder or greater than 1D of anisometropia, skip to Step 2.9: Final Evaluation and discontinue the subject from the trial
 

1.1.15	Subjective Spherical Equivalent Refraction	Perform Subjective Spherical Equivalent using maximum plus to best visual acuity.
1.1.16	Contact Lens Fitting	
Fit subject in contact lenses based upon the randomization schedule. Initial base curve should be selected as indicated in the fitting guide for each lens.
 
 
• If an acceptable contact lens fit cannot be obtained in either eye, skip to Step 2.9: Final Evaluation and discontinue the subject from the trial
 

1.1.17	Contact Lens Over-Refraction	Perform spherical over-refraction using maximum plus to best visual acuity
1.1.18	Contact Lens Power Adjustment (if necessary)	Modify contact lens power, based upon the Contact Lens Over-Refraction, if the subject gains 3 or more letters acuity
1.1.19	2 hour Waiting Period	Subjects released to waiting area for 2 hours

**FULL PROTOCOL TITLE: The Impact of Contact Lens Coefficient of Friction (CoF) on the Development of Lid Wiper Epitheliopathy (LWE)**

Visit 1.2 Note: Visit should be performed approximately 2 hours after lens insertion		
1.2.1	Visual Performance	Perform logMAR visual acuity
1.2.2	Oculus Keratograph	Perform the following procedures using Oculus Keratograph with the contact lens on eye, OD/OS 
 
• Non-invasive Tear Break Up Time (NITBUT)
 
• Tear Meniscus Height
 
• Video Contact Lens Fit
 

1.2.3	Ocular Surface Tear Collection	Collect 10µL surface tears using a microcapillary tube.
1.2.4	Contact Lens Removal	Remove the contact lenses and store in solution
1.2.5	Slit Lamp Exam with vital dye staining/LWE evaluation	Instill 1 drop of NaFL + Lissamine Green Combination Drop, wait 5 minutes, instill an additional drop, wait 1 minute, then evaluate slit lamp findings using the CCLRU grading scale and evaluate LWE

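### Step 1.1.12 is inverted: it discontinues subjects free of LWE and sends subjects with LWE on towards lens fitting, against the trial's own objective

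*Combined protocol and SAP*

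**What the plan says.** Section 1.0 (Objectives) defines the target as LWE "induced in subjects after contact lens fitting that do not have LWE at study enrollment". Section 2.0 (Background) gives the reason for the study: "it is currently unknown how quickly LWE may develop in patients after contact lens fitting". Section 7.0 makes the development of LWE after fitting, at 2 hours and at 1 week, the primary endpoint.

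Section 3.0 introduces its exclusions with "Potential study subjects cannot meet any of the following study exclusion criteria". Criterion 2 is current upper-lid LWE above 0.5 in height or width. The narrative closing that section says that subjects found not to have LWE are refracted and, if their refraction qualifies, fitted.

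The step table in Section 8.0 (Sequence of Events, Visit 1.1) applies the screen at Step 1.1.12. Its first branch is "If no LWE is observed in both eyes, skip to Step 2.9: Final Evaluation and discontinue the subject from the trial". Its second is "If LWE is observed in either eye, continue to" Step 1.1.13, which leads through refraction to randomised fitting at Step 1.1.16.

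**The concern.** The two branches at Step 1.1.12 are complete, agree with each other, and run opposite to the objective and the Section 3.0 narrative. This is not a stray word: one branch removes the subjects the trial is about, and the other separately moves the wrong group forward. Staff therefore hold two opposite instructions at the point where LWE is first assessed.

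What is at stake is the baseline population. Section 5.0 says that nothing is known about the time from fitting to LWE, and that the pilot's data will be used to size a larger trial. If the fitted subjects already had LWE, the grades at 2 hours and 1 week would mix existing with lens-induced LWE, and the pilot would not describe onset in LWE-free subjects. The randomised comparison between eyes (H01 and H02) would remain, but in a different population from the one stated.

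**Working it through.** No sample-size or error-rate formula applies. The check follows each baseline state through the competing rules.

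| Baseline finding | Step 1.1.12 | Section 1.0 and Section 3.0 narrative | Exclusion criterion 2 |
|---|---|---|---|
| No LWE in either eye | Discontinue | Target population; go on to refraction and fitting | Not excluded |
| Upper-lid LWE not above 0.5, one or both eyes | Continue | No route forward | Not excluded |
| Upper-lid LWE above 0.5, one or both eyes | Continue | No route forward | Excluded |

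The step is opposite to the objective and narrative in every row, and opposite to criterion 2 in the last row.

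**Literal step alone.** No subject free of LWE in both eyes reaches fitting: 0 of the planned 20. The only LWE-free eye that could be fitted is the fellow eye of a subject with LWE in the other eye.

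**Literal step plus criterion 2.** Reading the step as an upper-lid screen, as the Section 3.0 narrative does, only subjects with visible LWE not above 0.5 are fitted. The step itself names no lid. Read without that restriction, subjects with LWE on the lower lid only would also pass.

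**Does a later step catch it?** Four Visit 1.1 steps send a subject to Step 2.9:

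- Step 1.1.8: OSDI score of 23 or more
- Step 1.1.12: LWE
- Step 1.1.14: "refractive cylinder or greater than 1D of anisometropia, skip to" Step 2.9
- Step 1.1.16: "If an acceptable contact lens fit cannot be obtained in either eye, skip to" Step 2.9

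One of the four concerns LWE, and it is the inverted one. Two follow it, and 0 of those 2 concern LWE. The eligibility check at Step 1.1.6 is titled "Preliminary Review of Inclusion/Exclusion Criteria" and comes before the slit lamp exam.

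**Rescreening.** Section 5.0 allows up to 3 further screenings. A subject discontinued for having no LWE could return, and would pass the literal step only if LWE were then seen.

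**Threshold (minor).** Assume that the 0.5 in criterion 2 is a component grade; the criterion gives no unit. The Korb table in Section 8.0 defines the final score as the mean of height and width:

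- 0.5 on both components: (0.5 + 0.5)/2 = 0.50
- 0.5 on one component and 0 on the other: (0.5 + 0)/2 = 0.25

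Neither component exceeds 0.5, so criterion 2 admits both cases. Both scores lie in the table's mild range of 0.25 to 1.00, while its no-LWE grade is below 0.25. On that assumption, being free of LWE (Sections 1.0 and 3.0) and passing criterion 2 are different conditions.

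**The case against.** The strongest reply is that this is a clerical inversion. The objective, the narrative, criterion 2 and the endpoint all point the other way, Section 3.0 still bars anyone meeting an exclusion criterion, and nothing shows that staff followed the literal step. The figure of 0 of 20 is what the rule implies, not an estimate of what happened. All of that is fair. But Section 3.0 cannot bring back LWE-free subjects whom the step has discontinued, and the step table is the text that staff work from.

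A second reply is that the table was never a complete eligibility filter. The spherical refraction range and the staining exclusion have no exit there either, and Section 8.0 says that the Visit 1.1 assessment as a whole determines eligibility. This weakens the count of exits as evidence that criterion 2 went unenforced. It does not weaken the contradiction, because a missing exit is different from an instruction pointing the wrong way.

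Three narrower points stand:

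- Criterion 2 does not itself require LWE-free subjects to continue. For them the direct conflict is with Sections 1.0 and 3.0.
- The threshold arithmetic depends on 0.5 being a grade. A width of 0.5 mm would be grade 0. Section 8.0 also ties the Korb scale to photographs, which are taken after the screen.
- Step 2.10 records whether the subject completed the study; the plan does not say that it records why a subject was discontinued.

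**Conclusion.** The concern holds and must be fixed. As written, Step 1.1.12 contradicts the objective and the screening narrative for every baseline LWE state, and contradicts criterion 2 for upper-lid LWE above 0.5. Under the literal rule, 0 of 20 completers would be free of LWE in both eyes at baseline, and the stated objective could not be met.

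The contradiction rests on the text alone. The consequence for the data depends on which rule was applied, which the documents do not reveal. A drafting slip is the likelier explanation, but a reader cannot confirm from the plan that the analysed eyes were free of LWE at baseline. The threshold mismatch is secondary and conditional on reading 0.5 as a grade.

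**What to change.** 1. Reverse the two branches of Step 1.1.12, so that LWE-free subjects continue to Step 1.1.13 and subjects with excluding LWE are discontinued.
2. Define excluding LWE once, stating the threshold and its unit, the lid, and whether one or both eyes count. Use that definition in Section 1.0, in criterion 2 and the narrative of Section 3.0, and in Step 1.1.12. Reversal alone leaves LWE of 0.5 or less unsettled.
3. The Addendum (Statistical Analyses) is in the past tense, so a text correction cannot change who was fitted. Also report which screening rule was applied, the baseline LWE grade of each fitted eye, and how many LWE-free subjects were discontinued at this step.

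The cost is two bullets reversed and matching wording in the other places named. The report can draw on the Step 1.1.12 evaluations, the Step 1.1.13 baseline photographs of subjects who continued, and the Step 2.10 forms. If those forms give no reason for discontinuation, the last count needs a look through the screening source records. No extra subjects, visits or analyses are required.

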## FULL PROTOCOL TITLE: The Impact of Contact Lens Coefficient of Friction (CoF) on the Development of Lid Wiper Epitheliopathy (LWE)

Visit 2: 1-Week Follow Up ( $\pm 2$ days) Note: Subjects should report to Visit 2 wearing their study assigned soft contact lenses.		
2.1	History	Collect subject history, compliance and reported wearing time
2.2	Visual Performance	Perform logMAR Visual Acuity
2.3	Questionnaires	Administer the OSDI to the subject
2.4	Oculus Keratograph	
Perform the following procedures using Oculus Keratograph (lens on eye for CL patients, bare eye for non-CL patients, OD/OS)
 
 
• Non-invasive Tear Break Up Time (NITBUT)
 
• Tear Meniscus Height
 
• Video Contact Lens Fit
 

2.5	Ocular Surface Tear Collection	Collect 10 $\mu$ L surface tears using a microcapillary tube.
2.6	Contact Lens Removal	Remove the contact lenses and store in solution
2.7	Slit Lamp Exam with vital dye staining/LWE evaluation	Instill 1 drop of NaFL + Lissamine Green Combination Drop, wait 5 minutes, instill an additional drop, wait 1 minute, then evaluate slit lamp findings using the CCLRU grading scale and evaluate LWE
2.8	Digital Photography	Perform Digital Photography of the Lid Wiper region OD/OS
Final Evaluation		
2.9	Exit Visual Acuity	Perform Distance, High Contrast Visual Acuity using Snellen optotype with the patient's habitual correction.
2.10	Final Evaluation Form	Complete the final evaluation form and indicate if the subject successfully completed the study
2.11	Protocol Deviations	Ensure any protocol deviations have been recorded

The procedures involved in the study are common clinical procedures found in Optometry/Ophthalmology. LWE assessment will occur following installation of sodium fluorescein and lissamine green ophthalmic drops. The upper and lower lids will be photographed using a slit-lamp biomicroscopy and a camera.

Photographs will be de-identified and graded subjectively for LWE using the Korb scale (see below). Photos may also be analyzed for objective LWE grading using custom coding in MATLAB.

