## **7.0 Study Endpoints**

The primary study endpoints are as follows:

- Examine the development of LWE post-contact lens fitting at the following time points
  - 1-week post contact lens fitting
  - 2 hours after contact lens fitting

The secondary study endpoints are as follows:

- Examine the level of expression in ocular surface tear MMPs post-contact lens fitting at the following time points
  - Pre-contact lens fitting
  - 1-week post contact lens fitting
  - 2 hours after contact lens fit

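### No masking of the LWE grader to lens assignment is described, and by the visit table the 2-hour primary time point has only a live grade

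*Combined protocol and SAP*

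**What the plan says.** Section 7.0 sets the primary endpoint: "Examine the development of LWE post-contact lens fitting at the following time points", namely 1 week and 2 hours. Section 1.0 makes the tested contrast one between lenses, and so between a subject's two eyes, at each time point. On allocation it says "The eye receiving each lens will be assigned randomly". It also states the expected direction: "Contact lenses with a greater coefficient of friction will induce a greater amount of LWE than contact lenses with a lower coefficient of friction".

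In Section 8.0, LWE is graded by two routes.

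- **Live, at the slit lamp** (Steps 1.1.12, 1.2.5 and 2.7). After the dye drops the examiner is to "evaluate slit lamp findings using the CCLRU grading scale and evaluate LWE". No examiner is named and no masking is mentioned. At Step 1.1.16 the instruction was "Fit subject in contact lenses based upon the randomization schedule".
- **From photographs.** "Photographs will be de-identified and graded subjectively for LWE using the Korb scale (see below". An objective grade is optional: "Photos may also be analyzed for objective LWE grading using custom coding in MATLAB".

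Photography is a listed step at baseline (1.1.13) and at 1 week (2.8). Visit 1.2, the 2-hour assessment, lists none. Neither Section 8.0 nor the statistical addendum says which grade is the primary one.

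**The concern.** LWE is graded by eye on an ordinal scale, and the protocol tells the study team which eye should look worse. If the grader can learn which lens an eye wore, a small unconscious lean adds to one eye and not the other. Randomizing the eye and pairing within subject remove differences between people and between right and left eyes. They do not remove a lean that follows the lens, because that lean is part of the between-eye difference being tested.

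Two things are at stake: the tests of the two primary hypotheses, and the estimate that Section 5.0 intends for sizing a larger trial. A biased difference would carry over into that sample size.

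**Working it through.** The plan gives no effect size, SD or power, so there is no figure of its own to reproduce. The check is mainly a reading of the text, followed by an illustration of size.

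**1. What a grader would need in order to know the lens.** Lenses are removed before staining (Steps 1.2.4 and 2.6), so a lid image does not show the study lens. The grader needs three things: subject, eye and the randomization schedule.

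**2. What the plan withholds.**
- *Subject.* Section 16.0 gives each subject a two-digit ID in order of enrollment. Section 20.0 treats forms carrying only that ID as free of direct identifiers. By that usage an image labeled with ID and eye is de-identified.
- *Eye.* Nothing says it is hidden.
- *Schedule.* Nothing says it is kept from graders or examiners.
- *Order of grading.* Not stated.

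**3. Which time points the photographs cover.** By the visit table, baseline and 1 week have both a live grade and a photograph; 2 hours has the live grade only. The paragraph after the table says the lids will be photographed but names no visit. Even a generous reading of de-identification therefore does not clearly reach the 2-hour endpoint.

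**4. Illustration of size.** Inputs: n = 20 completers (Section 5.0); significance at 0.05 (Section 8.0), taken as two-sided. Assumed: no true lens effect, SD of the between-eye difference 0.5 to 1.0 grade, and a mean grader shift b of 0.125 or 0.25 grade. The final-score bands in the Korb table suggest steps of 0.25. A mean shift of 0.125 is then one step, in one eye, in half of the subjects: 10 × 0.25 / 20 = 0.125.

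For a paired t-test the noncentrality is δ = b√n / SD. The false-positive rate is the probability that a noncentral t with 19 degrees of freedom falls outside ±2.093.

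| Shift b | SD | δ | False positives |
|---|---|---|---|
| 0.125 | 0.50 | 0.125 × 4.472 / 0.50 = 1.118 | 19% |
| 0.125 | 0.75 | 0.745 | 11% |
| 0.125 | 1.00 | 0.559 | 8% |
| 0.25 | 0.50 | 2.236 | 56% |
| 0.25 | 0.75 | 1.491 | 29% |
| 0.25 | 1.00 | 1.118 | 19% |

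A simulated Wilcoxon signed-rank test gives similar values for the 0.25 shift: 54%, 27% and 18%.

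**5. The addendum's test.** The addendum names Friedman and Mann-Whitney tests for LWE. I simulated Mann-Whitney on 20 versus 20 eyes with normal data and paired-difference SD 0.5, so that each eye's SD is 0.5 / √(2(1 − ρ)), where ρ is the between-eye correlation:

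| ρ (assumed) | b = 0.125 | b = 0.25 |
|---|---|---|
| 0 | about 19% | about 56% |
| 0.5 | about 5% | about 26% |
| 0.7 | about 1% | about 10% |

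At SD 1.0 the rates are lower: about 8% and 19% at ρ = 0, and about 2% and 5% at ρ = 0.5. These low rates are not protection. Treating correlated eyes as independent makes the test reject only about 1% of the time at ρ = 0.5 with no shift at all. The estimated difference carries the whole shift b whichever test is used.

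**The case against.** The strongest reply is that silence is not an open design. The protocol never says that live grading is unmasked, nor that the person who fits the lenses also grades. Section 23.0 has the co-principal investigators overseeing other personnel, so a separate grader is possible. A reader might infer from the order of steps that one person fits, removes and grades; the documents do not establish that. The supportable statement is that no masking is described.

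Second, the route is narrow for photographs. Lenses are assigned to eyes at random and are off before the picture is taken. If subject identity really is removed, knowing right from left does not reveal the lens. This stands, and it limits the photograph concern to images that keep the study ID and are graded by someone with the schedule. The plan does not rule that case out. The argument gives no help with live grading, where the examiner has the subject present.

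Third, a reader might add knowledge of visit to the bias. Both eyes are graded at the same visit and the hypotheses compare lenses within a time point, so knowing the visit mainly affects change over time. It does not drive the primary contrast.

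Fourth, this is a pilot. That lowers the stakes, but Section 1.0 sets formal hypotheses and Section 8.0 a significance threshold, so the comparison will be read as a test.

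**Conclusion.** The concern holds as a gap with a plausible bias route, not as a demonstrated bias. In the text available, nothing masks the LWE grader to lens; the one safeguard is undefined de-identification of photographs; and the visit table gives the 2-hour primary time point no photograph.

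The size of any bias is unknown. The 8–19% and 19–56% ranges rest on assumed shifts, an assumed SD, a constant average lean across subjects and a paired t-test. It would be tempting to quote 19% and 56% as the trial's error rates. The documents do not support that: those are the values at the smallest SD assumed, and the addendum's Mann-Whitney test can fall well below them, even below 5%, when the eyes are correlated. What does not depend on these choices is that an expectation shift passes in full into the estimated difference between lenses. The change is worth making because it is cheap and closes the route.

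**What to change.** 1. Name the photograph grade as the primary LWE outcome.
2. Before grading, replace file names with random codes that hide subject, eye and lens, and also visit for the sake of change-over-time comparisons.
3. Grade all images in one random order, by a grader without access to the randomization schedule. Lock the grades before the code is broken.
4. At 2 hours, add the photograph step already used at the other visits. If that is not done, report the 2-hour live grade as not masked to lens.

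Items 1 to 3 cost a renaming list and a random order, with no extra staff. Item 4 adds a procedure and a few minutes to Visit 1.2. The addendum is written in the past tense. If grading is already complete, the report should state what the graders knew. Stored baseline and 1-week images could be re-graded under codes; the 2-hour grade could not be if no photographs were taken.
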